STUDY PROTOCOL

THE EFFICACY AND SAFETY OF FIRST LINE ANTI-EPILEPTIC DRUGS (AEDs) AS SUBSTITUTION THERAPY FOR CHILDREN WITH DRUG RESISTANT EPILEPSY

Protocol Number 22-09-1097

ABSTRACT

Background: Drug resistant epilepsy occurs around 30% of children with epilepsy. It is the failure to get seizure-free after combining two or more anti-epileptic drugs whether first- or second-line ones. Previous studies focus on the efficacy and safety between the two groups whether as add-on or substitution therapy mostly in newly diagnosed epilepsy children. However, the study that investigate first line Anti-epileptic Drugs (AEDs) as substitution therapy compared to second-line ones particularly among drug resistant epilepsy children is still lack. **Design**: It is an open-label, randomized controlled trial, which will be conducted in three referral hospitals in Jakarta, Cipto Mangunkusumo, Harapan Kita, and Fatmawati Hospital, from November 2022 until April 2023. The data will be collected from electronic medical record consisting of demographic, clinical characteristics, and brain CT scan or brain MRI, and diary cards that record daily drug consumption and adverse drug reaction. Self-administered QOLCE-55 questionnaire is used to assess the quality of life of the children. Furthermore, there will be EEG and laboratory examination prior and after intervention. The data will be recorded on Case Report Form that is filled by the researcher. Ethics committee approval is obtained from The Ethics Committee of The Faculty of Medicine, University of Indonesia-Cipto Mangunkusumo Hospital. Research permits would be issued by each institution where the study will take place.

Sample: There will be 100 participants, divided into 2 groups, the intervention and control. Fifty children in the intervention group will be treated with first line AEDs as the substitution therapy, while the other 50 participants in the control group will get second-line AEDs. The sample size is calculated based on the difference proportion of two independent groups.

Duration of the study: The study will take 14 weeks as a whole that consists of 6 phases including baseline, initial, titration, maintenance, tapering-of, stopping and another maintenance phase.

Introduction

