EEG recording results are categorized into:

- Normal: does not show of hypofunction/asymmetry/epileptiform waves
- Abnormal: shows a picture of hypofunction/asymmetry/epileptiform waves or a combination of 1 or more of these features

The subjects who show changes in their EEG are later grouped into groups of abnormal to normal or abnormalities that showed improvement. Abnormalities that show improvement, for example are hypofunction (slowing down) waves experience improvement or decreasing number of epileptiform waves.

Next, a proportion calculation is carried out in the form of the percentage to subjects who experience a change in the EEG and will be categorized into:

- Different : when a significant difference is shown in difference of proportion test of the group that reuses first line OAE line as substitution therapy and those that use standard therapy/
- Not different: when there is no significant difference is shown in difference of proportion test of the 2 groups.
- d. Difference in actual failure between the groups reusing first line OAE as substitution therapy and those taking standard therapy. Description of drug side effects in the form of frequency distribution and percentage of side effects in each group. Description of laboratory results in the form of frequency distribution and percentage of side effects in each group
- e. Factors contributing to decrease in seizure frequency (age, seizure onset, seizure type, family history of seizures, developmental delay, history of OAE, initial seizure frequency, initial EEG, structural brain abnormalities)

Sample size

The estimated sample size in this study was calculated using the different proportion formula for the 2 unpaired groups as follows ²⁹:

$$n1 = n2 = (\frac{Z_{\alpha}\sqrt{2PQ} + Z_{\beta}\sqrt{P1Q1 + P2Q2}}{P1 - P2})^{2}$$

Description:

n1 number of subjects who received the new drug (First Line OAE)

n2 number of subjects receiving standard drug (Second line OAE)

Alpha type one error (5%)

Zα alpha standard value 5% one-way hypothesis (1,96)

Beta type two error (20%)

Zβ beta default value 20% (0,84)

P2 proportion of decreased seizures on standard drugs (reference) for example 0.7

Q2
$$1-P2 = 1-0.7 = 0.3$$

P1-P2 difference in the proportion of reduced seizure that is considered significant between the new drug and the standard (defined by the researcher) for example 25% (0.25)

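### The secondary EEG outcome has no class for worsening, no restriction to children with an abnormal baseline EEG, no threshold for improvement, and no stated masking of the reader

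*Combined protocol and SAP*

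**What the plan says.** Outcome evaluation, item c, classes each EEG as normal or abnormal: "Normal: does not show of hypofunction/asymmetry/epileptiform waves", and abnormal if any of those features is present. Children whose EEG changes are then "later grouped into groups of abnormal to normal or abnormalities that showed improvement". Improvement is described by example: "Abnormalities that show improvement, for example are hypofunction (slowing down) waves experience improvement or decreasing number of epileptiform waves". The quantity compared between arms is "the percentage to subjects who experience a change in the EEG", tested by chi-square with a Fisher fallback (Statistical Analysis, item 1) and given a different / not different verdict.

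The surrounding sections leave four points open:

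- **Baseline EEG.** The inclusion and exclusion criteria contain no EEG requirement. Outcome evaluation, item e, lists initial EEG among the candidate factors ("initial seizure frequency, initial EEG, structural brain abnormalities").
- **Reading.** The Electroencephalography Examination section covers the two recordings, their length and when the report is available. It does not say who reads them or whether that person knows the arm or which recording came first. The Abstract states: "It is an open-label, randomized controlled trial".
- **Denominator.** None is stated for the EEG percentage.
- **Missing second EEG.** Under Study procedure, children whose intervention is ended become non-responders and are dropped. No rule says what happens to their EEG result.

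**The concern.** Differences in EEG are a named secondary objective with a formal test, so the definition decides what the test can show. There are three difficulties.

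1. **Classes.** Both change groups are favourable. A normal EEG that becomes abnormal, or an abnormality that gets worse, has no group. If the numerator is the two listed groups, worsening is pooled with no change. If it is any change, worsening is pooled with benefit. The text allows both readings.
2. **Denominator.** A child with a normal baseline EEG cannot enter either listed group. Each such child kept in the denominator adds a certain zero to both arms and pulls the two percentages together.
3. **Reading.** Improvement is a before/after judgement. With no threshold, a very small fall in epileptiform waves could count. In an open-label trial, a reader who knows the arm could lean one way without intending to.

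The stakes are lost power, a verdict that may mix benefit with deterioration, and a false-positive rate above the nominal 5%.

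**Working it through.** **Inputs.** The 50 children per arm and the 5% significance level come from Sample size and Statistical Analysis. The documents give no rate, effect size or power for the EEG outcome, so there is no plan figure to reproduce; the 50 per group was derived for responders. Every EEG rate below is an assumption.

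**1. Worsening.**

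- *Numerator is any change.* Suppose arm A has 40% improved and none worse, and arm B has 20% improved and 20% worse. Arm A scores 40% and arm B scores 20% + 20% = 40%, so a real difference disappears.
- *Numerator is the favourable groups only.* Suppose both arms have 30% improved, but 5% v 25% are worse. The score is 30% v 30%. A direct comparison of worsening at 50 per arm would have about 81% power (normal approximation).

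**2. Denominator.** Let f be the share with an abnormal baseline EEG, and let p1 and p2 be the improvement rates among those children. Over all children the rates are f·p1 and f·p2, so the difference is f·(p1 − p2). Restricting to abnormal baselines keeps p1 − p2 but leaves 50·f children per arm.

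Power is the sum of Bin(x; n, r1) × Bin(y; n, r2) over all pairs (x, y) for which the uncorrected chi-square reaches the two-sided 5% limit. Here r1 and r2 are the rates being compared. With p1 = 0.60 and p2 = 0.30:

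| f | All children, rates (n = 50) | Power | Abnormal only, n per arm | Power |
|---|---|---|---|---|
| 0.5 | 30% v 15% | 44% | 25 | 62% |
| 0.6 | 36% v 18% | 54% | 30 | 66% |
| 0.8 | 48% v 24% | 71% | 40 | 80% |
| 0.9 | 54% v 27% | 80% | 45 | 82% |
| 1.0 | 60% v 30% | 88% | 50 | 88% |

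A normal approximation points the same way: 43% v 57% at f = 0.5 and 71% v 78% at f = 0.8. With a smaller assumed effect of 50% v 25%, it gives 36% v 45% at f = 0.5, 59% v 64% at f = 0.8, and 74% for both at f = 1.

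**3. Reading.** Assume a true 30% improved in both arms. Suppose a fraction b of the non-improved EEGs in one arm only is read as improved. The observed rate in that arm is 0.30 + 0.70·b, compared with 0.30 at 50 per arm:

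| b | Observed rates | Shift | False-positive rate |
|---|---|---|---|
| 0 | 30% v 30% | 0 points | 5% |
| 0.05 | 33.5% v 30% | 3.5 points | about 7% |
| 0.10 | 37% v 30% | 7 points | about 11% |
| 0.143 | 40% v 30% | 10 points | 18% |
| 0.20 | 44% v 30% | 14 points | about 30% |

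**The case against.** The strongest reply is that much of this rests on silence and on assumed rates.

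- **Masking and denominator.** A reader might infer that the EEGs are read unmasked and that the percentage is taken over all children. The documents state neither. They leave both open, and that is as far as the point can go.
- **Dilution.** A reader might infer that the comparison is diluted. That needs normal baseline EEGs, and their share is not given. The definition of abnormal is broad and the children have drug-resistant epilepsy, so the share may be small. A normal class is needed anyway to score the second recording, and initial EEG as a factor need not mean normal v abnormal. At 90% abnormal the loss is about 2 points of power, and at 100% it is nil. Dilution also leaves the test valid under no difference.
- **Hidden harm.** A reader might infer that harm on EEG is invisible. If only favourable changes count, a child who worsens instead of improving still lowers that arm's percentage. Normal-to-abnormal shifts could be tabulated from the planned readings, and increased seizure frequency is analysed separately as treatment failure.
- **Importance.** This outcome is secondary and was never powered.

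These replies limit the size and certainty of the point. They do not supply a class for worsening, a numerator with one meaning, a threshold for improvement or a masked reading. Those gaps remain whatever the share of normal baselines.

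**Conclusion.** The point holds for the secondary EEG outcome. As written, the numerator has two possible meanings, and neither separates worsening from the other results. Nothing restricts the denominator to children who can improve, the judgement has no threshold, and reader masking is not specified in an open-label trial.

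The power cost of the unrestricted denominator depends on an unknown share. Under the assumed 60% v 30%, it is about 18 points if half the baselines are abnormal, 8 to 9 points at 80%, 2 points at 90% and none at 100%. The false-positive rate of about 11% to 18% applies only if a one-arm reading shift of 7 to 10 points occurs; the documents give no evidence that it will. They do not support saying that the EEGs are read unmasked, that dilution is certain, or that EEG harm cannot be seen at all. The primary outcome is unaffected. The change should be made before any post-intervention EEG is compared by arm.

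**What to change.** Amend Outcome evaluation, item c, and Statistical Analysis, item 1, as follows:

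1. Compare improvement among children with an abnormal baseline EEG.
2. Class each child as improved, unchanged or worse, by criteria fixed before reading.
3. Report worsening, including normal to abnormal, by arm among all children with both EEGs.
4. Have whoever already reads the EEGs score coded files with arm, identity and recording order hidden. This should cover the baseline recording too: under Study procedure, children are divided into groups before the baseline phase, so the baseline reading decides who enters the denominator when the arm is already known. Because that recording precedes the substitution drug, restricting on it keeps a fair randomised comparison if it is read this way.
5. State how children without a post-intervention EEG are handled, including those whose intervention was ended. The intention-to-treat rule in Statistical Analysis, item 3, is written for the treatment-failure comparison and is not extended to the EEG.

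The cost is plan wording and some file handling, with no extra children, visits or recordings. The downside is a smaller denominator for improvement: at 80% abnormal, 40 per arm instead of 50. Under the assumptions above, power is still no lower than with all children.

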The test is performed in hospitals' laboratory where the study take place and is done twice, at the baseline and post intervention phase. The order of the blood test consists of complete blood test, liver function test including alanine and aspartate transaminase, kidney function test including urea and creatinine, and also blood electrolyte that consist of natrium, kalium and calcium. The laboratory professional takes the blood from vein of the arm. The subjects are seated or lying down, accompanied by the parents, while for the younger children, they seat on his/her parents' lap or position that make them feel comfortable. Older children may be asked to make a fist and then will be tied by a rubber band around his/her arms. After that, the needle is inserted the needle until the blood is drawn. The laboratory worker will take the needle since the amount of blood is enough and puts an adhesive bandage over the site. The next step is analyzes of the sample and the result will be issued for about 1-2 days both printed or provided on the electronic medical record.

Electroencephalography Examination

The EEG examination is operated two times, at the baseline and post intervention phase, with high density machine (Caldwell Easy III) is done twice, pre- and post-intervention. The machine will operate for about 45 minutes including 5 minutes each for eye-open and eye-close in every subjects. Beginning with acquisition, EEG recordings use standard parameter to analyze brain activity at various frequencies to gain good quality and artefact-free result. The printed results of the EEG is available for about 4-7 days after the examination.

Data collection

All relevant data will be recorded, by nominated member(s) of the research team, on a case report form (CRF). Each participant will have a CRF and be assigned a unique identification number.

Baseline data

At entry into the study, the following baseline information will be recorded in the CRF:

- unique patient identification number contact telephone number and/or email address
- date of entry into the study
- eligibility for study entry based on inclusion/exclusion criteria
- age at study entry, in years and months
- gender
- weight and height
- seizure type (eg, generalized tonic clonic, absence, myoclonic and partial)
- the age at diagnosis and duration of epilepsy
- seizure frequency or average number of seizures per month

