- current anticonvulsant(s) with doses and formulation and its side effect (if presents)
- other medications and its side effect (if presents)

- first recognized seizure date
- prior EEG and laboratory which has been performed at the baseline phase
- physical examination

Follow-up data

Follow-up data will be collected during regularly scheduled clinic visits (per 2 weeks). This information will be obtained from the participants' diary card. Important information to be collected at follow-up will include:

- physical examination
- adverse drug reaction of the substitution therapy that happen
- seizure's frequency
- type of seizure
- complaint

Outcome evaluation

- a. The difference in responders was the difference in the percentage of responders in the group that used first line OAE again as substitution therapy and those that used standard therapy. Responders are subjects who experience a decrease frequency of seizure more than or equal to 50% of the initial seizure. Frequency of seizure is the number of seizures that occur within 1 month. In previous studies, it was said that the frequency of seizures was said to have decreased significantly or was said to respond if the seizures were reduced by 50% or more from the initial seizure. ^{19, 29} Based on this, researchers will categorize the frequency of seizures into:
 - Responder: there is a decrease in the frequency of seizures by 50% or more than before
 - Non-responder: namely the frequency of seizures remains or decreases but not up to 50% of the initial seizure frequency or the frequency is more than before

Furthermore, the proportion in the form of the percentage of respondents in the two groups is calculated and differentiated, therefore it is classified into two groups:

- Different : when a significant difference is shown in difference of proportion test of the 2 unpaired groups.
- Not different: when there is no significant difference is shown in difference of proportion test of the 2 unpaired groups.

- b. Differences in quality of life: quality of life assessment using QOLCE-55 instrument. The average of each function (cognitive, emotional, social and physical functions) and the average of the total functions are assessed. This variable is categorized into:
 - Different, if there is a difference in the average quality of life
 - Not different, if there is no difference in the average quality of life
- c. Differences in electroencephalography appearance

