This test will use 2 analyses known as intention to treat analysis and per-protocol analysis. Intention to treat analysis means that all research subjects who have been randomized are included in the analysis according to their initial allocation regardless of whether or not the subject is taking the drug/therapy being tested or a placebo, or whether these subjects died before taking the drug being tested. Subjects who did not

failure.

take medication, lost to follow-up, and who moved to another group, are considered failures of their original group.

Whereas per protocol analysis only includes subjects who complete the research to the end.

- 4. Analysis of the difference in time to achieve a decrease in seizure frequency with the chisquare test or if it does not meet the requirements, an alternative test is performed, namely the Mann-Whitney test
- 5. Analysis of clinical characteristics, side effects of OAE, and laboratory findings of complete blood count (hemoglobin, hematocrit, leukocytes, platelets, and type count), liver function (SGOT and SGPT), kidney function (urea and creatinine), and blood electrolytes (sodium, potassium, calcium, chloride) in pediatric epilepsy patients who are resistant to combination second OAE who re-use first line OAE as substitution therapy and who use standard therapy (secondary outcome). All existing data is processed and presented in a table consisting of mean and standard deviation or median and inter-quartile range, as well as frequency distribution.
- 6. Analyzing factors that affect the decrease in the frequency of late seizures (age, seizure onset, seizure type, family history of seizures, developmental delays, history of OAE, initial seizure frequency, initial EEG, brain structural abnormalities) in pediatric patients with resistant epilepsy combination of second line OAE who re-use first line OAE as substitution therapy (secondary outcome).

Data is categorical. Data is analyzed using Chi-square statistical test, if results do not meet the requirements then an alternative test will be performed, known as Fisher's multivariate test and further analyzed with multivariate test and logistic regression analysis. The significance level (α) is 5% and the research confidence level is 80%. Results will show statistically related if value of $p \le \alpha$ is obtained.

Ethics and dissemination

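### Paired blood samples are collected, but the laboratory safety summary does not use the child's own baseline, so entry abnormalities are not separated from new ones; the electrolyte lists also disagree

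*Combined protocol and SAP*

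**What the plan says.** **Sampling.** The Laboratory Examination section says the blood test "is done twice, at the baseline and post intervention phase". The Baseline data list puts the first result on the case report form: "prior EEG and laboratory which has been performed at the baseline phase". The same list records "current anticonvulsant(s) with doses and formulation and its side effect (if presents", so side effects of the drugs the child is already taking are noted at entry.

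**Outcome.** Outcome evaluation, d, specifies "Description of laboratory results in the form of frequency distribution and percentage of side effects in each group".

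**Analysis.** Statistical Analysis, item 5, covers blood count, liver function, kidney function and electrolytes. The results are to be "presented in a table consisting of mean and standard deviation or median and inter-quartile range, as well as frequency distribution". No test is named for these data.

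**Electrolytes.** The blood order in Laboratory Examination is for "blood electrolyte that consist of natrium, kalium and calcium". Item 5 analyses "blood electrolytes (sodium, potassium, calcium, chloride".

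**The concern.** The Secondary Objectives include describing laboratory findings linked to the drugs' adverse effects. That needs some way to tell a finding that appeared under the new regimen from one the child brought into the trial. Under the Inclusion criteria every child has had at least three months of combination therapy, so abnormal values at entry are plausible. The paired sample could make the distinction, but neither outcome d nor item 5 says that it will be used.

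The summaries are also hard to read for another reason. Ages run from 1 to 18 years, and testing is done in the laboratories of three hospitals. No age-specific or laboratory-specific reference range is named, so it is not clear what would count as abnormal.

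At stake is how the safety tables are interpreted. A percentage of laboratory side effects could consist largely of prior findings, and a real difference between the arms could look smaller in relative terms than it is.

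**Working it through.** The plan gives no rate of laboratory abnormality, so there is no figure to reproduce. The check is a comparison of the text, followed by an illustration with assumed rates.

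**Text comparison**

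| Item | EEG (outcome c) | Laboratory (outcome d, item 5) |
|---|---|---|
| Measured at baseline and post-intervention | Yes | Yes |
| Abnormal defined | Yes | No |
| Time point to be summarised | Both, through change | Not stated |
| Within-child change specified | Yes: abnormal to normal, or improved | No |

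The plan therefore specifies within-child change for one twice-measured outcome and leaves it out for the other.

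**Illustration**

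Inputs:
- 50 children per arm (Abstract).
- b, the assumed share abnormal at entry and still abnormal afterwards: 0 to 30%, equal in both arms.
- i, the assumed risk of a new abnormality among children normal at entry: 5% or 10%.

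Formulas:
- Share abnormal on the second sample = b + (1 − b) × i
- Share newly abnormal, of all children = (1 − b) × i
- Part of the abnormal second values that was already present = b / [b + (1 − b) × i]

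Worked case, b = 10% and i = 5%: 0.10 + 0.90 × 0.05 = 14.5%. Of this, 0.90 × 0.05 = 4.5% is new, and 0.10 / 0.145 = 69% was already present. In an arm of 50 that is 7.25 children counted against 2.25 newly abnormal.

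| b | i = 5%: second sample only | i = 5%: new | i = 5%: already present | i = 10%: second sample only | i = 10%: already present |
|---|---|---|---|---|---|
| 0% | 5.0% | 5.0% | 0% | 10.0% | 0% |
| 5% | 9.8% | 4.8% | 51% | 14.5% | 34% |
| 10% | 14.5% | 4.5% | 69% | 19.0% | 53% |
| 20% | 24.0% | 4.0% | 83% | 28.0% | 71% |
| 30% | 33.5% | 3.5% | 90% | 37.0% | 81% |

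**Effect on the comparison of arms**, assuming new abnormality of 5% in one arm and 15% in the other:

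| b | Second-sample shares | Risk difference | Risk ratio |
|---|---|---|---|
| 0% | 5.0% and 15.0% | 0.10 | 3.0 |
| 10% | 14.5% and 23.5% | 0.09 | 1.62 |
| 20% | 24.0% and 32.0% | 0.08 | 1.33 |
| 30% | 33.5% and 40.5% | 0.07 | 1.21 |

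The difference shrinks modestly and the ratio shrinks a lot.

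**Chance imbalance at entry.** With 10% abnormal at entry and 50 per arm, the standard error of the between-arm difference at entry is √(2 × 0.10 × 0.90 / 50) = 0.06, or 6 percentage points. Balance in expectation therefore leaves room for a visible imbalance in a trial of this size.

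**The case against.** The strongest reply is that the plan is silent rather than wrong. Several parts of it stand.

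- A reader might infer that the plan counts pre-existing abnormalities as side effects. The documents do not support that. They give no threshold, time point or counting rule, so such findings are neither counted nor excluded. Item 5 speaks of all available data, which could mean a table with both time points. However, two separate group summaries would still not show which children moved.
- Entry side effects of current drugs are recorded, and Follow-up data asks for reactions to the substitution drug. That shows some intention to separate old from new, but nothing ties it to the laboratory percentage.
- It is tempting to call the laboratory data the only objective safety marker. Physical examination is also recorded, at baseline and at the two-weekly visits.
- It is tempting to say that a flat mean would hide children who move out of range. The plan also asks for a frequency distribution, so it does not rely on means alone.
- Precision is not a general argument for change scores. With equal variances, SD(change) / SD(post) = √(2(1 − r)): 0.63 at r = 0.8, 0.89 at r = 0.6, 1.00 at r = 0.5 and 1.10 at r = 0.4. The documents give no r, and no test is planned. The case for change rests on interpretation.
- Randomisation balances age, laboratory and entry abnormalities between arms in expectation. This protects the comparison from systematic bias. It does not correct the inflated percentages or the diluted ratio.
- On chloride, a reader might conclude that there will be no data. The documents do not show which list is in error, only that the two differ.

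**Conclusion.** The point holds as an omission. Paired samples are planned, but neither outcome d nor item 5 uses the child's own baseline or defines a laboratory side effect, so entry abnormalities are not separated from new ones. If only second samples were counted, the percentage would read 5.0% to 33.5% for 5% new abnormality and 0 to 30% persistent entry abnormality. A true risk ratio of 3.0 would read 1.62 to 1.21 at 10 to 30% entry abnormality. These figures rest on assumed rates, on full persistence of entry abnormalities and on equal entry rates in the arms. With no entry abnormalities the problem disappears.

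The electrolyte mismatch is a separate inconsistency and needs no assumption. The outcome is secondary, descriptive and untested, so the point is minor to moderate.

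**What to change.** In outcome d and item 5:

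1. For each parameter, report within-child change from baseline by arm, and a shift table by arm (low, normal or high at baseline against post-intervention), using each hospital laboratory's age-specific reference range.
2. Count a laboratory side effect only when the value moves to a worse reference-range category than at baseline or, if already abnormal, worsens by a margin stated in advance. Without a stated margin, trivial movement in an already abnormal value would count.
3. Report the number of missing second samples by arm. This matters because Study procedure treats children whose intervention is ended as drop-outs, and the plan does not say whether they give the second sample.
4. Make the electrolyte lists in Laboratory Examination and item 5 agree, either by removing chloride from the analysis or by adding it to the order.

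The cost is wording, a set of reference ranges from three laboratories and additional tables. Both samples are already planned, so items 1 to 3 need no extra blood draw. The small downside is that children without a second sample cannot enter the change or shift tables, which is why they must be counted openly.

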P1 proportion of reduced seizure on the new drug (the proportion of reduced seizure on the standard drug in addition to the minimal difference that is considered significant)= 0.7 + 0.25 = 0.95

Q1
$$1 - P1 = 1 - 0.95 = 0.5$$

P
$$(P1 + P2) / 2 = (0.95 + 0.7) / 2 = 0.825$$

Q
$$1-P = 1-0.825 = 0.175$$

In this study, it was found that the proportion of seizure reduction on standard drugs was 70%.³⁰ Therefore the equation:

$$n1 = n2 = \left(\frac{1,96\sqrt{2(0,825)(0,175)} + 0,84\sqrt{(0,95)(0,5) + (0,7)(0,3)}}{0,25}\right)^2 = 49,56 = 50$$

$$n\ 2\ groups=100$$

Based on the formula above, 100 research subjects are required. An additional of 10% from the total number of subjects are needed as there is a possibility of those dropping out, therefore a total of 110 subjects are needed in this study.

Statistical Analysis

- 1. Analysis of differences in the proportion of responders (primary outcome), differences in EEG appearance (secondary outcome) in pediatric epilepsy patients who are resistant to the combination of second line OAE between those who reused first line OAE as substitution therapy and those who used standard therapy. Data type is categorical. Data is analyzed the Chi-square statistical test, if it does not meet the requirements then an alternative test is performed, known as Fisher's multiple test. The significance level (α) is 5% and the research confidence level is 80%. If p value ≤ α is obtained, this means H0 is rejected, which means that there is a difference seen in seizure frequency between reusing first line OAE as substitution therapy and standard therapy.
- 2. Analysis of differences in the mean quality of life with an unpaired T test if the data distribution is normal or Mann-Whitney if data distribution is not normal
- 3. To assess drug effectiveness, the analysis used was the difference in actual failure between those using first line OAE as substitution therapy and those using standard therapy (primary outcome). Formula:

$$ARR = CER - EER$$

CER: the incidence of increased seizure frequency in the standard therapy group ERR: the incidence of increased seizure frequency in the group in substitution therapy with 1st line OAE The increase in seizure frequency in this study shows therapy

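### The stated 80% power is not shown to be the power of the primary test: the 70% used for sizing is not tied to the 50% responder endpoint, and at the plan's own rates the power is about 92%

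*Combined protocol and SAP*

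**What the plan says.** Outcome evaluation, item a, defines the primary endpoint: "Responders are subjects who experience a decrease frequency of seizure more than or equal to 50% of the initial seizure". Frequency is the count over one month. Statistical Analysis, item 1, compares the proportion of responders between arms by chi-square, with a Fisher alternative. Under the Inclusion criteria, every child has drug-resistant epilepsy and at least 3 months of combination therapy.

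The Sample size section describes the quantity differently. P2 is the "proportion of decreased seizures on standard drugs (reference) for example 0.7", P1 is 0.7 + 0.25 = 0.95, and the 25 points are chosen by the researcher. On the source it says "it was found that the proportion of seizure reduction on standard drugs was 70" per cent, citing reference 30, a national guideline on epilepsy management. The section gives no 50% threshold, does not call these children responders, and names no population for the 70%. The responder definition cites two other references (19 and 29).

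Type II error is set at 20%. The section prints Q1 = 1 - 0.95 = 0.5 and arrives at 49.56, rounded to 50 per arm.

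**The concern.** A power statement belongs to one endpoint in one population. Here the sizing quantity and the tested quantity have different names and different sources, and nothing links them. If the 70% does not measure a fall of at least 50% in drug-resistant children, the 80% says nothing definite about the primary comparison.

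The variance also depends on where the rates lie. The pair 0.70 and 0.95 sits close to 1, where the variance is small. The same 25-point difference in mid-range needs more children.

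The power matters for interpretation because Outcome evaluation, item a, classes a non-significant result as showing no difference between the arms. That rule is open to question at any power, but a reader needs the true power to judge such a result.

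**Working it through.** **Inputs, all from the Sample size section.** z = 1.96 for alpha (labelled one-way, but 1.96 is the two-sided 5% value, and I use it as printed); z = 0.84 for 80% power; P2 = 0.70; P1 = 0.95; mean P = 0.825, Q = 0.175; 50 per arm before the dropout allowance.

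**The plan's formula.** n per arm = ((1.96·√(2PQ) + 0.84·√(P1Q1 + P2Q2)) / (P1 - P2))².

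**Step 1: reproduce the plan.** With the printed Q1 = 0.5:
- 1.96·√(2 × 0.825 × 0.175) = 1.0532
- 0.84·√(0.95 × 0.5 + 0.7 × 0.3) = 0.6952
- n = (1.7484 / 0.25)² = 48.91, against the printed 49.56, a difference of less than one child.

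**Step 2: correct Q1 to 0.05.**
- 0.84·√(0.95 × 0.05 + 0.7 × 0.3) = 0.4263
- n = (1.4795 / 0.25)² = 35.02, so 36 per arm.

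**Step 3: power at 50 per arm.** Inverting the formula, power = Φ((√n·(P1 - P2) - 1.96·√(2PQ)) / √(P1Q1 + P2Q2)).
- Control 0.70: (1.7678 - 1.0532) / 0.5074 = 1.408, power 92%.
- Control 0.40, P1 = 0.65: (1.7678 - 1.3842) / 0.6837 = 0.561, power 71%.

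**Step 4: a range of control responder rates.** Only 0.70 stands in the plan's sizing; the other rates are assumptions. The 25-point difference is kept, except in the last column. The exact column is the uncorrected two-sided chi-square by binomial enumeration.

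| Control rate | n per arm for 80% | Power at 50 (formula) | Power at 50 (exact) | Difference detectable at 80%, 50 per arm |
|---|---|---|---|---|
| 0.10 | 43 | 86% | 88% | 23 points |
| 0.15 | 49 | 81% | 82% | 25 points |
| 0.20 | 54 | 77% | 77% | 26 points |
| 0.30 | 61 | 72% | 74% | 27 points |
| 0.40 | 62 | 71% | 73% | 28 points |
| 0.50 | 58 | 74% | 75% | 27 points |
| 0.60 | 49 | 81% | 82% | 25 points |
| 0.70 | 36 | 92% | 95% | 22 points |

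For a fixed 25 points the variance is symmetric about a mean rate of 0.5. Control 0.15 therefore gives the same power as 0.60, and the lowest power falls near a control rate of 0.375. Power is below 80% only for control rates from about 0.16 to 0.59.

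**Step 5: two further cases.** If enrolment were cut to the corrected 36 per arm, power at control rates of 0.40 to 0.50 would be 57 to 59%. If the ratio 0.95/0.70 is held instead of the 25 points, power at 50 per arm is 66% at control 0.60, 44% at 0.50 and 30% at 0.40.

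**The case against.** The best defence is that the wording is loose and no second outcome is meant. Outcome evaluation, item a, says earlier studies counted frequency as meaningfully decreased, or the patient as responding, at a reduction of 50% or more. Statistical Analysis, item 1, describes a positive responder test as a difference in seizure frequency. So the 70% may simply be a responder rate. This stands, and it rules out three stronger readings.

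- A reader might infer that the 70% counts any decrease, so that it caps the responder rate and the trial is underpowered. No text says that it counts any decrease.
- A reader might infer that 70% is a general-epilepsy figure, because the Abstract states "Drug resistant epilepsy occurs around 30% of children with epilepsy". The link is only numerical. The Introduction defines drug resistance as failure to become seizure-free, so the complement of 30% would concern seizure freedom, a stricter outcome than a 50% fall. In that source population, the responder rate would then be at or above 70%.
- A reader might infer that any control rate below about 0.60 leaves power under 80%. Step 4 shows that this is false at 0.15 and below.

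The Introduction also reports that about 43% and 31% of children did not remit on topiramate and levetiracetam, so about 57% and 69% did. At those control rates power would be 78% and 91%. They do not settle the matter: they concern remission on the drugs to be replaced, which enrolled children already take while drug resistant.

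Finally, the loss is modest if the 25 points are kept: at worst about 71%, with a detectable difference of at most about 28 points. That is fair, though the loss is larger if the relative effect is the one that carries over.

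**Conclusion.** The point holds as a failure to show, not as proof of low power. The 80% is not supported on either reading. If 0.70 is the control rate of a fall of at least 50% in drug-resistant children, 50 per arm has about 92% power (95% exact) for 0.95 against 0.70, and the stated figure is too low because of the Q1 slip. If the control responder rate is something else, power for 25 points depends on that rate. It is below 80% between about 0.16 and 0.59 and reaches its minimum of about 71% (73% exact) near 0.40.

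The first result follows from the plan's own inputs. The second rests on assumed control rates, a fixed 25-point difference, a two-sided 5% test and 50 analysed per arm. What reference 30 measured, and in whom, cannot be seen from the documents.

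**What to change.** In the Sample size section:

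1. Define P1 and P2 as the proportion of drug-resistant children with a decrease of at least 50% in monthly seizure frequency, matching Outcome evaluation, item a.
2. State whether the 70% from reference 30 is that rate, and in which population. If it is not, give a value for this endpoint and population, or say that none is available.
3. Correct Q1 to 0.05 and restate the result: 36 per arm by the formula, about 92% power at 50 per arm for 0.95 against 0.70.
4. Keep 50 per arm. The correction should not be used to cut enrolment while the control rate is unsettled.
5. Replace the single 80% claim with a short table of power for 25 points and of the difference detectable at 80% power, over a range of control responder rates.

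The cost is wording and one small table, with no extra enrolment. The downside is that the stated power becomes conditional and may look less favourable: about 71 to 81% for control rates of 0.20 to 0.60.
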